Hypothesis 1: We will identify the units of analysis that show the strongest relative loading onto 3 reward-relevant symptom assessments in the areas of anhedonia, impulsivity, and mania across patients and controls.

Specific Aim 2: To investigate the predictive validity of reward learning units in a naturalistic follow-up study.

Hypothesis 2a: Relative weights for each unit of analysis for each symptom assessment area derived in Aim 1 will be used to predict the presence of anhedonic, manic and impulsive symptoms as assessed via phone interview at 3- and 6-month follow-up intervals. We predict that our units of analysis will have significant incremental predictive validity in predicting these domains while controlling for baseline severity.

Hypothesis 2b: Individuals who present at baseline with depressive symptoms but show an elevated response bias and enhanced PE signaling will show less symptom improvement following SSRI treatment in a naturalistic design (i.e., there is no treatment component to the study, but it is expected that many patients recruited through clinics will be receiving SSRI treatment).

III. SUBJECT SELECTION

a. Inclusion and exclusion criteria

General Exclusion Criteria

- 1) Suicidal ideation where outpatient treatment is determined unsafe by the study clinical interviewer. These patients will be immediately referred to appropriate clinical treatment;
- 2) Pregnant women or women of childbearing potential who 1) have not completed a negative urine pregnancy test prior to the MRI scan and/or 2) are seeking to become pregnant or believe that they may be pregnant

- 3) Serious/unstable medical illness (e.g., cardiovascular, renal, endocrine, neurologic disease);
- 4) Clinical or laboratory evidence of hypothyroidism;
- 5) History of seizure disorder, history or current diagnosis of dementia, score < 26 on the MMSE at screening;
- 6) History or current diagnosis of the following DSM-IV psychiatric illness: organic mental disorder, schizophrenia, schizoaffective disorder, delusional disorder, psychotic disorder NOS, patients with mood congruent or mood incongruent psychotic features
- 7) Lifetime history of stimulant dependence (e.g., cocaine, amphetamines)**;
- 8) Current use of Methylphenidate (Ritalin) and other ADHD medications with dopaminergic effects**;
- 9) Patients who have had electroconvulsive therapy (ECT) in the past 2 years;
- 10) Failure to meet standard MRI safety requirements;

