Participants will have an opportunity to receive a “mock scan” that simulates the conditions of the actual scanner at the McLean Brain Imaging Center. In particular, participants will experience the sounds (i.e., repetitive metallic thumping), feel (i.e., enclosed within the scanner with head coil), and sights (i.e., will see what fMRI equipment looks like). During the process, participants will be trained to limit movement. Specifically, participants will be played a movie while they are in the mock scanner, and if there is too much movement, the movie will stop. Consequently, through repeated trial and error, participants will learn to reduce head movement, which may jeopardize the usability of scans. In addition to habituating to the scan environment, participants will also have an opportunity to ask questions about the process. Any and all questions will be addressed openly and honestly. It is expected that a mock scanner will be available at the McLean Imaging Center by the end of January.

Follow Up Interviews

Participants will be re-assessed at 3- and 6-month follow-up interviews, which will take place at the Center for Depression, Anxiety, and Stress Research at McLean Hospital. Information collected during these sessions will allow us to test the utility of our behavioral and neuroimaging measures in predicting subsequent symptom severity. Each follow-up time point will consist of an interview that will re-assess clinical measures previously administered during the behavioral session. This includes the IDS (Rush et al., 1996), SF-36 (McHorney et al., 1993), PSS (Cohen et al., 1983) ATRQ (Chandler et al., 2009), GHQ, MCQ, BISS (Bowden et al., 2007), BDI-II (Beck, et al., 1996); CGI-S and CGI-I (Guy, 1976), SF-36 (McHorney et al., 1993), Q-LES-Q (Endicott et al., 1993), MASQ (Watson et al., 1995), TEPS (Gard et al., 2007), ATRQ (Chandler et al., 2009), BIS (Patton, Stanford & Barratt, 1995), YMRS (Young et al., 1978); Richards Delay Discounting Task (Richards et al., 1999) as well as the Longitudinal Interval Follow-up Evaluation (LIFE; Keller et al., 1987; the LIFE assesses symptomatology, treatment intensity, and psychosocial functioning for naturalistic studies) The SCID will not be re-assessed as part of these sessions. Each follow-up interview session is expected to take approximately 2 hours.

Debriefing

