Behavioral Data: For the PRT, the main dependent variable will be Reward Learning, as operationalized as the increase in response bias during the final block relative to the first block [= DResponse Bias = Response Bias(Block 3) - Response Bias(Block 1)]. This variable was selected because it has been repeatedly linked to current and future anhedonic symptoms (Pizzagalli et al., 2005, 2008b; Vrieze et al., 2013a).

b. Study endpoints

Not applicable

c. Statistical methods

Data analyses will proceed in two stages. First, descriptive statistics and graphs will be used to assess the presence of skewness and/or outliers in the four main variables of interest (*Aim 1*). Continuous/quantitative variables will be appropriately transformed. Similarly, covariates in regression analyses (*Aims 1 & 2*) will be summarized to determine whether a continuous versus categorical representation is the most appropriate. For these regressions, the analytic approach will address the type of outcome (e.g., continuous or discrete) and the functional relationship between covariates and outcome (e.g., linear versus non-linear). The second stage will involve the analyses of the central hypotheses in *Aims 1-2*:

Aim 1: For Hypothesis 1, we will first use multiple regression to examine the relationships between our behavioral and neuroimaging measures and the symptom domains of anhedonia, mania and impulsivity, which will be assessed using the symptom severity collected during session 2. Standard multiple regression techniques will be used to identify the optimal weights for each unit of analysis (MRS, fMRI striatal PE signals, ERP FRN, PRT response bias). Additionally, to take advantage of the correlations between the three symptom domains and to potentially improve predictive accuracy, a single multivariate analysis (canonical correlation analysis) will be used to assess a separate set of weights reflecting the contribution of each unit in relationship to all three symptom domains simultaneously. For ease of interpretation, the latter analysis will be based on the first pair of canonical variables. Models will be fit using SAS PROC CANCORR.

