Aim 2: For Hypothesis 2a, symptom inventories collected during follow-up interviews will be used to investigate incremental predictive validity of each unit of analysis in predicting subsequent symptoms while controlling for baseline severity. For these models, our behavioral and neuroimaging measures will be modeled using the relative weighting derived from the analyses described in aim 1. For quantitative measures (e.g., depressive and anhedonic symptoms), linear mixed effects models will be used. These models incorporate random subject effects to account for correlation among the repeated outcome measures (months 0, 3, 6); models will be fit using SAS PROC MIXED. Hypotheses concerning frequency measures (e.g., frequency of impulsive/risky behaviors) will be tested in a similar way. Models will be fit using SAS PROC GENMOD. Statistical tests and confidence intervals will be based on the “sandwich” estimator of standard errors to ensure that correlation among repeated assessments and overdispersion is accounted for.

d. Power analysis

Sample size and power calculations

Sample size determination was calculated based on observed effect sizes derived from prior studies that in our lab. Effect sizes were calculated using $\alpha = 0.05$ (two-tailed) for (1) detecting relationships between reward learning variables across different unit of analyses and reward-related symptoms (e.g., anhedonia, mania); and (2) to predict symptom severity measures in a naturalistic follow-up study. Based on these estimates and allowing for 15% patient attrition or data loss, the sample will be: 80 treatment-seeking individuals with mood disorders recruited from three clinics as well as 32 psychiatrically healthy controls.

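### The Aim 2 model lists month 0 as an outcome while controlling for baseline severity and names no tested contrast, so the size of the follow-up effect, and under one reading its test, depends on an unstated model

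*Combined protocol and SAP*

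**What the plan says.** Section VI.c, Aim 2, opens by naming the inventories from the follow-up interviews as the data for Hypothesis 2a. The aim is "incremental predictive validity of each unit of analysis in predicting subsequent symptoms while controlling for baseline severity". The predictors carry over from Aim 1: "our behavioral and neuroimaging measures will be modeled using the relative weighting derived from the analyses described in aim 1". For quantitative outcomes the same paragraph then specifies linear mixed models: "These models incorporate random subject effects to account for correlation among the repeated outcome measures (months 0, 3, 6"). Frequency outcomes are to be handled similarly in PROC GENMOD, and tests and confidence intervals use sandwich standard errors.

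Other sections place the outcome after baseline. Hypothesis 2a (section II.a) concerns symptoms "as assessed via phone interview at 3- and 6-month follow-up intervals". Section V.a, Follow Up Interviews, says that data from those two visits "will allow us to test the utility of our behavioral and neuroimaging measures in predicting subsequent symptom severity".

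The plan does not define month 0. It is most naturally session 2: the follow-up interviews "will re-assess clinical measures previously administered during the behavioral session", and Aim 1 relates the units of analysis to symptom domains "which will be assessed using the symptom severity collected during session 2". This is an inference. No section gives the fixed effects, the form of baseline adjustment, the time terms or the contrast that tests Hypothesis 2a. Section VI.b (study endpoints) is marked not applicable.

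**The concern.** Month 0 cannot be subsequent to itself. If the month-0 score is both an outcome and the baseline covariate, the month-0 rows say nothing about incremental prediction, because the covariate reproduces the outcome exactly. What those rows do to the result depends on terms that the plan leaves open. They may only rescale the coefficient, or they may move the tested contrast away from zero when there is no true effect.

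The Aim 1 weights make the second case more than theoretical. They are fitted to session-2 severity, so the weighted score is likely to correlate with month-0 severity. Hypothesis 2a is a claim about incremental prediction, and the plan promises confidence intervals as well as tests, so both the effect size and the test need a defined meaning.

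**Working it through.** **The plan's own power figure.** Section VI.d gives 80 patients, two-sided alpha 0.05 and a predictive correlation of size 0.41. By Fisher z, atanh(0.41) x sqrt(77) - 1.96 = 0.4356 x 8.775 - 1.96 = 1.862, so power is 0.969. The bias-corrected form gives 0.970 and the noncentral F gives 0.978. The stated figure of above 0.97 reproduces. It is a calculation for one correlation and does not involve the mixed model.

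**Notation.** g is the true effect of the score at follow-up given baseline, R the score-baseline correlation, and stability the slope of follow-up on baseline severity. The score is constant within subject.

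**Reading 1: month-0 score as covariate, one score effect pooled over months 0, 3 and 6.** With complete data and a random intercept, the score coefficient equals that from regressing the subject mean (Y0 + Y3 + Y6)/3 on score and Y0. Given Y0, the month-0 component has zero score effect and zero residual. So

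pooled effect = (0 + b3 + b6)/3 = (2/3) x (b3 + b6)/2,

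and the standard error shrinks by the same factor. In one simulated dataset (n=80) the estimate was 0.1563 (SE 0.0565) pooled against 0.2344 (SE 0.0847) with months 3 and 6 only, with t = 2.767 in both.

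**Reading 2: score-by-time added, one common baseline slope.** The contrast is follow-up minus month 0, so the common baseline term cancels. The score slope is R at month 0 and stability x R + g at follow-up:

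contrast = g - (1 - stability) x R.

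At R = 0.41 the bias is -0.6 x 0.41 = -0.246 for stability 0.4, -0.4 x 0.41 = -0.164 for 0.6, and -0.2 x 0.41 = -0.082 for 0.8. It is zero at R = 0 or stability 1.

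**Reading 3: baseline-by-time and score-by-time together.** The month-0 score effect is zero and the follow-up effects are recovered.

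**Simulation.** These inputs are assumed, not in the documents: n=80 analysed, four units with inter-unit correlation 0.2, stability 0.6, g = 0.30, residual SD 0.8 and within-subject residual correlation 0.5. R = 0.41 is borrowed from the healthy-subject correlation in section VI.d, so R = 0.20 and 0 are also shown. Fits were random-intercept REML with sandwich standard errors, 1500 replicates per cell. The estimates below use weights fitted in the same sample.

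| Model | Estimate | Power |
|---|---|---|
| Months 3 and 6 only, complete data | 0.303 | 0.934 |
| Reading 1, complete data | 0.202 (ratio 0.667) | 0.934 |
| Reading 2, complete data | 0.123 | 0.31 |
| Reading 3, complete data | 0.303 | 0.934 |
| Months 3 and 6 only, 15% lose both follow-ups | 0.303 | 0.893 |
| Reading 1, 15% lose both follow-ups | 0.186 (ratio 0.615) | 0.887 |
| Months 3 and 6 only, 15% lost at each follow-up | 0.300 | 0.911 |
| Reading 1, 15% lost at each follow-up | 0.187 (ratio 0.624) | 0.905 |

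The 15% is the plan's own figure ("allowing for 15% patient attrition or data loss"). Under reading 1 with complete data, the decision was the same in all 1500 datasets, but the 95% interval covered the follow-up effect 58% of the time, against 94% with months 3 and 6 only. With 15% losing both follow-ups, decisions differed in 1.1%. Type I error was 6 to 7% in both models. For log-link counts the estimates were 0.211 and 0.302 (ratio 0.70), with power above 0.99 in both.

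Type I error of the reading 2 contrast at stability 0.6:

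| R | External weights | Weights fitted in-sample |
|---|---|---|
| 0.41 | 47% | 54% |
| 0.20 | 14% | 23% |
| 0 | 6% | 16% |

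The external-weight column isolates the effect of the month-0 rows. The excess at R = 0 comes from in-sample weighting alone. At R = 0.41 with in-sample weights, the error is 76% at stability 0.4 and 21% at 0.8.

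**Other readings** (same n, different assumed effects; 25 simulated datasets each). Relative to the follow-up effect, the pooled estimate was about 0.93 when the covariate was a different, correlated measure, about 1.34 with no baseline covariate, and about 0.35 with a random slope.

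**The case against.** The opening sentence of the Aim 2 paragraph names the follow-up inventories as the data and subsequent symptoms as the target. A competent analyst could read the list of months loosely and fit a valid model. That clause does favour the intended analysis, but it conflicts with the list of outcomes in the same paragraph and does not settle how baseline or time enters.

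A reader might infer that the plan's effects will be understated by a third. The documents do not support that. The 2/3 needs the same month-0 score as outcome and covariate, one pooled effect, a random intercept only, a linear model and complete data. The plan states neither pooling nor the form of the covariate. Baseline severity is not tied to one instrument either: the QIDS-C and BDI-II are taken at session 1 and many scales at session 2.

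It is also fair that reading 1 leaves the significance test intact, and that the large error rates under reading 2 rest on assumed stability and on an R from a different population. Both points stand as limits on size. They do not remove the need to state the model, since the readings run from attenuation through inflation to an invalid test.

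Finally, the plan names no frequency instrument. The LIFE is listed at follow-up but not at session 2. If it supplies the counts, there is no month-0 value and the duplication does not arise for them.

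**Conclusion.** The concern holds as an internal conflict and an unspecified contrast, not as a proven bias. Month 0 is listed as an outcome against the plan's own target of later symptoms, and nothing fixes the tested coefficient.

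If the month-0 score is both outcome and covariate:

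- A pooled score effect reports 2/3 of the follow-up effect and interval under the conditions above, about 0.61 to 0.62 with 15% loss and about 0.70 for log-link counts. The test is essentially unchanged.
- A score-by-time contrast with a common baseline slope is biased by -(1 - stability) x R whenever R is not 0 and stability is below 1. With external weights, stability 0.6 and R 0.41, type I error is about 47%.

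The direction across all plausible readings is not fixed. A reader might also infer that the study is underpowered for Aim 2. This point gives no support for that, because the stated power above 0.97 reproduces and does not depend on the model in question.

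**What to change.** In section VI.c, Aim 2, replace the list of three months with months 3 and 6 as the only repeated outcomes, in both PROC MIXED and PROC GENMOD. Enter the session-2 value of the same measure as covariate only, and visit as a factor. Name the effect of the Aim 1 weighted score over months 3 and 6 as the test of Hypothesis 2a.

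An equivalent option is to keep month 0 as an outcome, include both baseline-by-time and score-by-time terms, and name the follow-up contrast. For any frequency measure without a session-2 value, name the baseline severity measure that will serve as covariate. State in the text that month 0 means session 2, if that is intended.

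The cost is wording and code, with no new data. In the simulations above, the weighted-score test loses no power against the pooled model.

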For group comparisons, multiple past studies using the PRT have found that unmedicated MDD subjects exhibited reduced reward learning compared to controls (Cohen's $d: -0.70$; Pizzagalli et al 2008c; Cohen's $d: -0.61$; Vrieze et al 2013a). In contrast, euthymic individuals with bipolar disorder had significantly higher reward learning relative to controls (Cohen's $d: 0.72$) (Pizzagalli et al 2008b). For the reinforcement learning task proposed for our fMRI study (Pessiglione et al 2006), we found that, relative to healthy controls, MDD subjects had significantly lower accuracy during reward learning (Cohen's $d: -1.54$). These effect sizes translate to power >0.98 for detecting group differences with the proposed sample size. For dimensional approaches, past studies have shown a strong large effect for the relationship between reward learning and anhedonic symptoms in BPD patients ($r = -0.59$). Moreover, among healthy subjects, reward learning predicted anhedonic symptoms 30-40 days later ($r = -0.41$, $p < 0.05$). In light of these effect sizes, a total of 80 individuals with mood disorders leads to a power of >0.97 of (1) detecting relationships between units of analysis and reward-related symptoms (e.g., anhedonia, mania), and (2) predicting clinical outcome in the naturalistic follow-

up study. Finally, in an fMRI study probing reward processing, unmedicated MDD subjects showed weaker activation than controls to gains in the caudate ($d = -0.98$) and left Nac ($d = -0.73$) and left putamen ($d = -0.78$) during reward anticipation (Pizzagalli et al 2009), yielding a mean effect size of -0.87. In light of an average ES of 0.83 in the fMRI study, a total of 80 individuals with mood disorders and 32 healthy controls leads to a power >0.97 of detecting group differences.

VII. RISKS AND DISCOMFORTS

The risks associated with participation in this study are minimal, and every possible precaution is being taken to further reduce potential risks, as described below:

Behavioral component. We foresee no risks from the behavioral tasks required for the proposed research.

Genetic component.

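### Sandwich standard errors for the Aim 2 frequency outcomes have no stated small-sample correction; with 68 to 80 patients and assumed overdispersed counts, a 5% Wald test would reject about 6 to 12% of the time

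*Combined protocol and SAP*

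**What the plan says.** Section VI.c (Statistical methods, Aim 2) of the combined protocol and SAP treats two kinds of follow-up outcome for Hypothesis 2a. Quantitative measures go to linear mixed models with random subject effects in PROC MIXED, over months 0, 3 and 6. For counts it says: "Hypotheses concerning frequency measures (e.g., frequency of impulsive/risky behaviors) will be tested in a similar way". It continues: "Models will be fit using SAS PROC GENMOD". The next sentence rests tests and confidence intervals on the sandwich "estimator of standard errors to ensure that correlation among repeated assessments and overdispersion is accounted for".

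The section does not mention a finite-sample correction, a t or F reference, degrees of freedom, or a choice between Wald and score tests.

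Section VI.d (Power analysis) sets the sample at "80 treatment-seeking individuals with mood disorders recruited from three clinics as well as 32 psychiatrically healthy controls", after "allowing for 15% patient attrition or data loss". The nominal level is two-sided 0.05. The same section ties the follow-up prediction to the 80 patients. It does not say whether controls enter the Aim 2 models.

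**The concern.** The sandwich estimator is robust to correlation and overdispersion only asymptotically in the number of subjects. In a finite sample the fitted model is pulled toward each subject's own data, most strongly for subjects with high leverage. The residuals that feed the variance are therefore too small, and so is the standard error. Overdispersed counts make this worse, because a few subjects with large counts carry much of the information.

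Impulsivity is one of the three symptom domains in Hypothesis 2a, and the plan's example of a frequency measure is impulsive or risky behaviour. If the plan is followed with the standard estimator and a Wald test, a claim of incremental predictive validity in that domain would face a looser threshold than the stated 5%, and the intervals would cover less than 95%.

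**Working it through.** **Inputs from the documents.** Two-sided alpha 0.05, 80 patients and 15% loss (VI.d); up to three assessments (months 0, 3, 6), sandwich standard errors and PROC GENMOD (VI.c); four continuous units of analysis, or a weighted composite of them, plus baseline severity (VI.c); 32 controls.

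**The plan's own figures first.**
- Evaluable patients: 80 x 0.85 = 68.
- If controls enter with the same loss: (80 + 32) x 0.85 = 95; without loss, 112.
- Power for follow-up prediction with r = -0.41, Fisher z: Phi(atanh(0.41) x sqrt(n - 3) - 1.96). At n = 80: Phi(0.4356 x 8.775 - 1.96) = Phi(1.86) = 0.969, which matches the stated >0.97 to rounding. At n = 68: Phi(0.4356 x 8.062 - 1.96) = Phi(1.55) = 0.940.

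The plan gives no error rate for the sandwich tests beyond the nominal 0.05, so that has to be simulated.

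**Assumptions, because the documents are silent.** Counts are gamma-Poisson with mean 1 to 5 and overdispersion from none to heavy. There are one or four subject-level predictors (normal, skewed or binary), with adjustment for baseline and visit in most runs. Some runs use months 0, 3 and 6 with a predictor-by-time term. The model has a log link and independence working correlation. The predictor tested has no effect. Each scenario has 3,000 datasets, so Monte Carlo error is about 0.4 to 0.6 points.

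**Estimators.**
- Standard sandwich: `V = A (sum of U_i U_i') A`, where `A` is the inverse information and `U_i = D_i'(y_i - fitted_i)`; test |b|/SE > 1.96.
- Mancl-DeRouen: replace each residual vector by `(I - H_i)^-1 (y_i - fitted_i)`, where `H_i` is the subject's leverage block; t reference with df = N minus the number of parameters.
- Generalized score test, for comparison.

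**Selected results (rejection of a true null at nominal 5%).** Moderate overdispersion means gamma variance 1 between subjects and 0.3 between visits, with mean count 2. All rows use two visits.

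| Scenario | N | Sandwich, Wald z | Mean SE / true SD | Mancl-DeRouen, t | Score |
|---|---|---|---|---|---|
| No overdispersion, mean 3, one predictor | 68 | 7.1% | 0.95 | 4.7% | 4.9% |
| same | 80 | 6.4% | 0.96 | 4.5% | 4.7% |
| Moderate, balanced binary predictor | 68 | 7.0% | 0.93 | 5.6% | 5.1% |
| Moderate, one continuous predictor | 68 | 8.8% | 0.91 | 5.3% | 4.1% |
| same | 80 | 7.7% | 0.91 | 5.0% | 4.3% |
| Moderate, four continuous predictors | 68 | 10.3% | 0.86 | 5.0% | 5.8% |
| same | 80 | 8.2% | 0.89 | 4.6% | 5.0% |
| same | 95 | 9.1% | 0.89 | 5.4% | 5.7% |
| same | 112 | 8.1% | 0.91 | 5.2% | 5.0% |

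**Over all scenarios.**
- Standard sandwich with Wald z: 7.0 to 11.6% at N = 68 and 6.4 to 10.7% at N = 80. Moderate overdispersion with a continuous predictor gives 7.7 to 10.7%; heavy overdispersion gives 9.5 to 11.6%.
- N = 95 to 112: 6.1 to 9.1%.
- At N = 68 to 80, the corrected sandwich with t gives 4.0 to 6.6% and the score test 4.1 to 5.8%.
- A separate simulation under similar assumptions gave 6.5 to 10.8% uncorrected at N = 68 to 80, 5.9 to 9.1% at N = 112, and 4.1 to 6.4% corrected.

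**Hand check.** Mean SE over true SD runs from 0.80 to 0.96. If the estimate is normal, the rejection rate is 2 x (1 - Phi(1.96 x ratio)). A ratio of 0.96 gives 2 x (1 - Phi(1.88)) = 6.0%, and 0.80 gives 2 x (1 - Phi(1.57)) = 11.7%. This agrees with the simulated range.

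**The case against.** Several points on the other side are fair.

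- **The plan does not say the estimator is uncorrected, or that tests are Wald tests.** A reader might infer that the plan chose an uncorrected sandwich with a normal reference. The documents do not support that: they are silent on all three. Basing tests and intervals on standard errors does read more naturally as Wald inference, and score tests would hold close to 5%, but that is an inference.
- **No particular error rate follows from the documents.** No count outcome is designated among the follow-up instruments, and the count mean and overdispersion are not given. A reader might infer a doubled false-positive rate. That appears only at the upper end, with heavy overdispersion or with several predictors at the smaller sample size.
- **The sample may be larger.** The follow-up section does not restrict the interviews to patients, and Hypothesis 1 spans patients and controls. Including controls shrinks the inflation but does not remove it.
- **The first analysis stage checks skewness and outliers and transforms variables.** This may lower predictor leverage, but it does not correct the variance estimator.
- **Materiality is limited.** This is an observational study with no formal endpoints, and the point touches one class of outcomes in its second aim.

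A reader might also extend the point to the PROC MIXED models. The sandwich sentence follows the GENMOD sentence, and the mixed models already carry random subject effects, so the text does not clearly apply it there.

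What survives is that the stated assurance about correlation and overdispersion is asymptotic, the sample is small, and nothing in the plan compensates.

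**Conclusion.** The point holds as a gap in specification with a measurable consequence. If the frequency outcomes are analysed with the standard sandwich and a Wald z test, a nominal 5% test would reject a true null roughly 6 to 12% of the time at 68 to 80 patients, or about 6 to 9% at 95 to 112 subjects. Under the null, the simulated 6.4 to 11.6% at 68 to 80 patients corresponds to coverage of 88.4 to 93.6% for a nominal 95% interval.

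The direction of the bias was the same in every scenario. Its size depends on the assumed gamma-Poisson counts, overdispersion, number of predictors and Wald test. Because the plan itself anticipates overdispersion and its predictors are continuous, the mildest scenarios are not the most natural ones. This is a cheap improvement and does not call Aim 2 into question.

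**What to change.** For the frequency outcomes, add to section VI.c that confidence intervals and tests use a bias-corrected sandwich (for example Mancl-DeRouen) with a t reference, with degrees of freedom equal to the number of subjects minus the number of mean-model parameters. Generalized score tests are an acceptable alternative for the p-values only, since intervals built on uncorrected standard errors would remain too narrow.

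State whether the sandwich sentence also covers the PROC MIXED models, and apply the correction there only if it does. State whether controls enter the Aim 2 models, because this sets the number of subjects.

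The cost is a change of procedure or some added code, plus wider intervals. From the ratios above, the widening is about 1/0.96 = 1.04 (4%) at the mild end and 1/0.80 = 1.25 (25%) under heavy overdispersion.
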